### 10.5.2. Assessment of expectedness of an SAE by the CI

The CI or delegate(s) will also assess all related SAEs for expectedness with reference to the criteria in Table 5.If the event is unexpected (i.e., it is not defined in the protocol as an expected event) it will be classified as a related and unexpected SAE.

The CI will undertake review of all SAEs and may request further information from the clinical team at site for any given event(s) to assist in this.

## 10.5.3. Provision of SAE follow-up information

Following reporting of an SAE for a participant, the participant should be followed up until resolution or stabilisation of the event. Follow-up information should be added to the original SAE form. Once the SAE has been resolved, all critical follow-up information has been received and the paperwork is

**Table 4**: Categories of expectedness

Category	Definition
Expected	An adverse event that is consistent with known information about the trial related procedures.
Unexpected	An adverse event that is not consistent with known information about the trial related procedures.

complete, a copy of the final version of the completed SAE form must be submitted to the Trial Office and the original kept in the ISF.

## 10.6. Reporting SAEs to third parties

The independent Data Monitoring Committee (DMC) will review any SAEs at their meetings.

The Trial Office will submit a progress report to the Research Ethics Committee (REC) and the University of Birmingham (UoB) Research Governance Team (RGT) annually starting 12 months after the date of the favourable opinion was given. An electronic copy should be emailed to the REC within 30 days of the end of the reporting period.

The Trial Office will report all events categorised as Unexpected and Related SAEs to the Research Ethics Committee (REC) and UoB Research Governance Team (RGT) within 15 days of being notified. Details of all Unexpected and Related SAEs and any other safety issue which arises during the trial will be reported to the PIs. A copy of any such correspondence should be filed in the ISF and Trial Master File (TMF).

## 10.7. Urgent Safety Measures

If any urgent safety measures are taken, the Trial Office shall immediately, and in any event no later than 3 days from the date the measures are taken, give written notice to the REC of the measures taken and the reason why they have been taken.

## 10.8. Follow-up of pregnancy outcomes for potential SAEs

Since live birth is the primary outcome in the trial, congenital abnormalities or birth defects will be routinely collected and monitored. Data on congenital anomalies or birth defects will be recorded on the Clinical Pregnancy Outcome CRF.

## 11.DATA HANDLING AND RECORD KEEPING

## 11.1. Source data

Source data is defined as all information in original records and certified copies of original records of clinical findings, observations, or other activities in a clinical trial necessary for the reconstruction and evaluation of the trial. In order to allow for the accurate reconstruction of the trial and clinical management of participants, source data will be accessible and maintained.

Some data variables may be entered directly onto the CRF:

- Patient Reported Outcome Measures

Other data is non-CRF based

- Healthcare science sub-study videos and slides
- Qualitative process evaluation and bioethics study transcripts

\_\_\_\_\_

Source data is kept as part of the participants' medical notes generated and maintained at site.

Table 5: Source data in UNiTY

Data	Source
Participant Reported Outcomes	The original participant-completed CRF is the source. Electronic versions will be stored on the trial database. Paper versions will be stored with the participant's trial record at site with copies provided to the trial office.
Lab results	The original lab report (which may be electronic) is the source and will be kept and maintained, in line with normal local practice. Information will be transcribed onto CRFs.
Imaging/videos	The source is the original imaging usually as an electronic file. Data may be supplied to the Trials Office as a password-protected, anonymised, copy of the electronic file, or as an interpretation of the imaging provided on a CRF. Where data is interpreted, the CRF onto which it is transcribed becomes the source. Copy of the CRF should be provided to the trial office.
Clinical event data	The original clinical annotation is the source document. This may be found on clinical correspondence, or electronic or paper participant records. Clinical events reported by the participant, either in or out of clinic (e.g., phone calls), must be documented in the source documents.
Recruitment	The original record of the randomisation is the source. It is held on BCTU servers as part of the randomisation and data entry system.
Withdrawal	Where a participant expresses a wish to withdraw, the conversation must be recorded in the source documents.
Healthcare Science substudy	The slides and videos obtained for this sub-study are the source data.  Analysis will be performed directly on this material.
Qualitative transcripts	The audio file onto which the interview is recorded is the source documentation

\_\_\_\_\_

11.2. Case Report Form (CRF) completion

The CRFs will include (but will NOT be limited to) the Forms shown in **Error! Reference source not found.** 

**Table 6**: Case report forms in UNiTY

Form Name	Schedule for submission
Informed Consent Form (one for each partner)	Prior to randomisation
Screening CRF	Prior to randomisation
Baseline CRF	Prior to randomisation
Baseline participant questionnaire: - EQ-5D-5L	Prior to randomisation
Treatment CRFs: - IVF treatment CRF - IUI treatment CRF - Laboratory CRF - Frozen Transfer CRF	During or as soon as possible after treatment
Outcomes CRF: - Post-treatment CRF	8 weeks after treatment starts (defined as the first day of ovarian stimulation) in order to capture all potential complications/outcomes.
Outcomes CRF: - Clinical Pregnancy outcome CRF	As soon as possible after each follow up assessment time point (19 months and 25 months post randomisation)
Outcome participant questionnaires  - EQ-5D-5L (one questionnaire to be completed for each partner)  - CSQ-8 (one questionnaire to be completed for each partner)  - Health resource use (one questionnaire to be completed per couple)	As soon as possible after each follow up assessment time point (during the first treatment cycle of IUI and/or IVF, 19 months and 25 months post randomisation)
Non-trial treatment form	During or as soon as possible after treatment
Natural pregnancy notification CRF	As soon as possible after becoming aware of participant's pregnancy
Serious Adverse Event Form	If expedited: emailed within 24 hours of site research team becoming aware of event If non-expedited: emailed within 4 weeks of site research team becoming aware of event
Change of Status Form	As soon as possible after the point of reduced participation
Deviation Form	As soon as possible after a protocol deviation has occurred

A CRF should be completed for each couple or individual participant as documented at the top of each document. CRFs repeat to account for multiple treatment cycles and multiple pregnancies.

In all cases it remains the responsibility of the PI to ensure that the CRF has been completed correctly and that the data are accurate. This will be evidenced by the signature of the PI, or delegate(s). The Site Signature & Delegation Log will identify all those personnel with responsibilities for data collection.

The delegated staff completing the CRF should ensure the accuracy, completeness and timeliness of the data reported. This will be evidenced by signing and dating the CRF.

Data reported on each CRF will be consistent with the source data and any discrepancies will be explained. Missing and ambiguous data will be queried. Staff delegated to complete CRFs will be trained to adhere to GCP requirements and trial-specific guidelines, which will be provided separately.

All CRFs will be entered into REDCap by site teams. Paper copies of the forms are provided only for sites who wish to complete forms in an area with no immediate internet access.

The following guidance applies to data and partial data, on REDCap and if paper copies of forms are used:

- Only CRFs provided by the Trial Office should be used.
- Entries should be made in dark ink and must be legible.
- Any errors should be crossed out with a single stroke, the correction inserted and the change initialled and dated.
- Time format all times should be in accordance with the 24hr clock
- Trial-specific interpretation of data fields where guidance is needed additional information will be supplied
- Entry requirements for concomitant medications (generic or brand names) generic names should be used where possible
- Missing/incomplete data should be clearly indicated all blank fields will be queried by the Trial Office
- Repeat laboratory tests the data used to inform clinical decisions should always be supplied.
   If a test is repeated it is either to confirm or clarify a previous reading. Confirmatory tests should use the original test values.
- Protocol and GCP non-compliances should be reported to the Trial Office on discovery.

Data for the UNiTY sub-studies, namely qualitative transcripts, and videos and slides of semen samples, will not have a CRF. Analysis will be directly performed on source data. Collection and processing of this data will be done in accordance with GCP, the relevant sections of this protocol and separate trial-specific instructions.

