## **Complications**

The following outcomes will be assessed:

i.) for the first IVF treatment within 450 days post randomisation for a period of 60 days following the date of FSH injection;

- ii.) for the first three IUI cycles within 450 days post randomisation for a period of 30 days following the date of ovarian stimulation for partial or cancelled cycles, or date of insemination for complete cycles.
  - Ovarian hyperstimulation syndrome (mild, moderate, severe);
  - Pelvic infection;
  - Bleeding post oocyte retrieval (IVF only);
  - o Admission to High Dependency Unit (HDU)/ Intensive Therapy Unit (ITU), standard ward admission, A&E visit or Outpatient review.

The following outcomes will be assessed at 28 days post birth (or patient's discharge date from hospital whichever is sooner).

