# 9. TRIAL PROCEDURES

# 9.1. Schedule of assessments

**Table 2:** Schedule of Assessments

Trial process	Month 0	Month 2	Month 4	Month 6	Month 9	Month 19	Month 25	Ad hoc
Screening	Х							
Consent	Х							
Baseline data collection	Х							
Randomisation	Х							
IUI Treatment CRF		Х	Х	Х				
IVF Treatment CRF		Х			X 			
Laboratory CRF		Х	Х	Х	X 			
Frozen Transfer CRF		Х						
Clinical Pregnancy outcome						Χ	X 	X 
Post Treatment CRF						X 	X 	
EQ-5D-5L	Х	X 				Х	X 	
Health Resource use		X 				Χ	X 	
CSQ-8		X 				Χ	X 	
Complications - collected on Post Treatment CRF		х	х	х	х	x	X 	
Assessment of adverse events	Throu	ghout partic	ipant's time	on trial until	60 days after	the outcome	of the cycle is	known
Change of Status								Х
Protocol Deviations								Х
Non-trial treatment CRF								Х

Natural Pregnancy Notification					X 
Qualitative process evaluation	Х				
Qualitative bioethics				Х	

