## Additional notes on Error! Reference source not found.

- Months 2-6 are an approximation for when couples will have the three cycles of IUI; this process may be longer.
- X Couples randomised to IUI but progress to IVF as part of clinical care. All couples randomised to IUI cannot progress to subsequent IVF treatment until 270 days (approximately 9 months) post randomisation.
- X to measure outcomes for all couples who conceive within 450 days of randomisation.
- X³- one Clinical Pregnancy Outcome CRF to be completed per positive pregnancy test.
- X- to be completed for each pregnancy conceived during the trial outside of IVF or IUI treatment.
- X one Post-Treatment CRF to be completed 8 weeks after treatment starts (defined as the first day of ovarian stimulation).
- The qualitative sub-studies will approach participants at the indicated timepoints, but their interviews will happen in the subsequent weeks.
- X- measured during the first treatment cycle of IUI and/or IVF. The ideal timepoint during a treatment cycle to collect these questionnaires is between the date of insemination and the date of the pregnancy test for couples undergoing IUI, and between the date of embryo transfer and the date of the pregnancy test for couples undergoing IVF.

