## 10.3. Adverse event reporting in UNiTY

The reporting period for AEs in UNiTY will be from the day the trial intervention starts until 60 days after the cycle outcome is known. For an unsuccessful cycle (i.e. biochemical pregnancy was not detected) SAEs should be reported for 60 days following the negative pregnancy test. For cycles resulting in pregnancy, SAEs should be reported for 60 days after the pregnancy outcome is known (i.e. live birth, still birth, termination or miscarriage). SAEs should only be reported for trial related treatments, with the exception of the first IVF cycle in the IUI arm. Any non-trial treatment related SAEs should be recorded in the medical notes but not reported to the trial office.

The safety profile for the trial population and interventions are well established, so although it is recommended that the severity, seriousness, and causality of all AEs for both participants and offspring should be recorded in the relevant medical notes, a strategy of targeted reporting of AEs will not affect the safety of participants. Related AEs will be captured as complications within the primary and secondary outcome measures. Only serious, related, and unexpected adverse events, beyond the routine expectations and known risks for fertility treatment, will be reported as SAEs.

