### 10.4.1. Serious Adverse Events not requiring reporting to the Trial Office

At whatever time they occur during an individual's participation, from commencement of intervention up to 60 days after the cycle outcome is known, only serious and related SAEs will be reported to the trial office. SAEs that do not fall into these categories will be recorded on follow up CRFs.

All events which meet the definition of serious must be recorded in the participant notes, including the causality and severity, throughout the participant's time on trial, including follow-up, but for trial purposes these events do not require reporting on the SAE Form. Such events are "safety reporting exempt". They will be recorded on the treatment CRFs as part of trial follow-up.

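### The Post-Treatment CRF falls due on day 56, but the first-IVF complication window runs to day 60, so an IVF form completed on time and not updated can miss late non-serious events

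*Protocol*

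**What the plan says.** Three parts of the protocol bear on this.

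- **The outcome.** Section 8.2.2.1 (Complications) assesses OHSS, pelvic infection, bleeding after oocyte retrieval, and admissions or visits. For IVF the window is "for the first IVF treatment within 450 days post randomisation for a period of 60 days following the date of FSH injection". For the first three IUI cycles it is "for a period of 30 days following the date of ovarian stimulation for partial or cancelled cycles, or date of insemination for complete cycles".
- **The form.** The schedule of assessments in section 9.1 has a row reading "Complications - collected on Post Treatment CRF".
- **The timing of the form.** Note X5 to that schedule asks for "one Post-Treatment CRF to be completed 8 weeks after treatment starts (defined as the first day of ovarian stimulation"). Table 6 in section 11.2 gives the same timing and adds a purpose: "8 weeks after treatment starts (defined as the first day of ovarian stimulation) in order to capture all potential complications/outcomes".

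Section 10.3 explains why this form matters for non-serious events: "Related AEs will be captured as complications within the primary and secondary outcome measures". Section 14.2.2 says that complications will be tabulated by group without an expected formal analysis.

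**The concern.** Table 6 says that eight weeks is late enough to capture every potential complication. For IVF it is not, because the outcome defined in section 8.2.2.1 is still open when the form falls due. A site that fills in the form on the due date, and does not return to it, has reported on a shorter period than the outcome definition requires.

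The shortfall is one-sided. It affects the IVF arm and the first IVF cycle after IUI, but normally not the IUI cycles. Comparing complication rates between the arms is secondary clinical objective 3 (section 2.2.1). The IVF complication table should therefore cover the 60 days that it will be described as covering.

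**Working it through.** **Inputs**

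- Form due: 8 weeks after the first day of ovarian stimulation (section 11.2, Table 6; section 9.1, note X5).
- IVF window: 60 days after FSH injection (section 8.2.2.1).
- IUI window: 30 days after stimulation for partial or cancelled cycles, 30 days after insemination for complete cycles (section 8.2.2.1).
- Letrozole starts on cycle day 2, and insemination follows the trigger by 24 to 40 hours (section 7.1.1).
- Assumption, not in the protocol: the IUI trigger falls on cycle day 12 to 18.

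**IVF, form at 8 weeks**

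- Due day = 8 × 7 = 56, counting from the first stimulation day.
- If FSH starts on that day, the window ends on day 60.
- Gap = 60 − 56 = 4 days (days 57 to 60).
- Share of the window = 4 / 60 = 6.7%. This is a share of days. The protocol gives nothing on when events occur, so it cannot be turned into a share of events.
- Section 8.2.2.1 does not say which FSH injection starts the clock. If the reference date is *k* days after the first stimulation day, the gap is 60 + *k* − 56 = 4 + *k* days. The protocol gives no value for *k*, so only the 4-day figure (*k* = 0) can be traced to it.

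**IUI, form at 8 weeks**

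- Partial or cancelled cycle: the window ends on day 30, which is 26 days before the form is due.
- Complete cycle: window end, in days from stimulation start = insemination cycle day − 2 + 30.
- A trigger on cycle day 12 to 18 plus 24 to 40 hours puts insemination on cycle day 13 to 20.
- Window end = 13 − 2 + 30 = day 41, to 20 − 2 + 30 = day 48.
- Margin before the form is due = 56 − 48 = 8 days, to 56 − 41 = 15 days. There is no gap.
- An IUI window would pass day 56 only if insemination came more than 56 − 30 = 26 days after stimulation started.

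**Alternative reading: the month-19 tick is a second collection**

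- Latest first-IVF window, with IVF starting on day 450: 450 + 60 = day 510, or 510 / 30.44 = 16.8 months.
- Month 19 = 19 × 30.44 = day 578.
- Margin = 578 − 510 = 68 days. On this reading nothing is uncovered.

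**After the fix**

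- 9 × 7 = day 63, which is 63 − 60 = 3 days past the window when *k* = 0. It therefore covers *k* up to 3. Beyond that, the condition of not before day 60 after the first FSH injection governs.

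**The case against.** The strongest reply is that eight weeks is a submission date, not a cut-off for ascertainment. The 60-day outcome definition is unchanged. Safety follow-up also goes on: "The reporting period for AEs in UNiTY will be from the day the trial intervention starts until 60 days after the cycle outcome is known". Clinical events must be in the source documents (section 11.1), and CRFs must agree with source (section 11.2). Query rules and site guidance sit in separate documents that are not shown. All of this stands, and it limits the claim to forms that are completed on schedule and not updated. But a form signed on day 56 agrees with the notes as they were on that day, and no text in the protocol asks sites to reopen it for days 57 to 60.

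A second reply is that other routes exist. Serious related events go on an SAE form (section 10.4.3) and OHSS admissions go on the relevant CRFs (section 10.4.2). For the remaining serious events, "SAEs that do not fall into these categories will be recorded on follow up CRFs". This also stands, and it leaves only non-serious events. Outpatient and emergency visits are collected as resource use too (section 15.1), but for the economic analysis.

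A third reply is that the complications row of the schedule is ticked at months 2, 4, 6, 9, 19 and 25, so later collection may already be planned. The protocol does not settle this. If the month-19 tick is a real second collection of treatment complications, the gap closes.

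A reader might go further and infer that the schedule contradicts its own note X5, and that the complications ticks should be collapsed into one entry per treatment cycle. The text does not support that. The complications row carries no X5 mark. Its month-25 tick carries X2, which concerns couples who conceive within 450 days. The later ticks may therefore schedule the antenatal, intrapartum, post-partum and neonatal complications in section 8.2.2.1, and removing them could open a larger gap than the one being closed. The form's own row does show X5 at months 19 and 25, which is awkward, but the table was extracted from PDF and its columns should not carry much weight.

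**Conclusion.** The mismatch is real and minor. For IVF, the due date in Table 6 and note X5 cannot deliver the purpose that Table 6 gives for it. The uncovered period is 4 of 60 days, assuming that FSH starts on the first stimulation day, that the form is completed on its due date and not updated, and that the later schedule ticks are not a second collection of the same items. What could be missed is a non-serious complication or visit on about days 57 to 60 of an IVF cycle.

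A reader might infer that safety data will be lost or that the arm comparison will be biased. The documents do not show either. Event timing is not given, serious events are routed elsewhere, and no test, margin or decision rests on the complication table. The consequence is limited to an IVF table that may not match its own 60-day definition.

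**What to change.** In Table 6 (section 11.2) and note X5 (section 9.1), for IVF cycles, replace the eight-week due time with: *9 weeks after the first day of ovarian stimulation, and not before day 60 after the first FSH injection*. Naming the first injection also removes the doubt about which one starts the clock. Leave IUI cycles at 8 weeks, and leave the complications ticks in the schedule as they are.

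The cost is that IVF forms arrive about one week later. The wording goes into a protocol amendment (REC/HRA approval first if it is classed as substantial, section 18), with form scheduling and site guidance updated to match. No extra visit or procedure is needed.

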#### 11.3. Participant completed questionnaires

Participant questionnaires can be completed using the participant's favoured mode of communication (letter, telephone, email, online), with a reminder if no response is provided within 2 weeks.

## 11.4. Data management

Processes will be employed to facilitate the accuracy and completeness of the data included in the final report. These processes will be detailed in the trial specific Data Management Plan and include the processes of data entry, data queries and self-evident corrections on trial data.

Data entry will be completed by the sites via a REDCap trial database. The data capture system will conduct automatic range checks for specific data values to ensure high levels of data quality. Queries

\_\_\_\_\_

will be raised via the trial database, with the expectation that these queries will be completed by the site within 30 days of receipt. Overdue data entry and data queries will be routinely requested.

